10.3.1 Definition of AE

AE definition

- An AE is any untoward medical occurrence in a clinical study participant, temporally associated with the use of study intervention, whether or not considered related to the study intervention.
- NOTE: An AE can therefore be any unfavorable and unintended sign (including an abnormal laboratory finding), symptom, or disease (new or exacerbated) temporally associated with the use of a study intervention.
- NOTE: For purposes of AE definition, study intervention (also referred to as Sponsor's product) includes any pharmaceutical product, biological product, vaccine, device, diagnostic agent, or protocol specified procedure whether investigational (including placebo or active comparator product) or marketed, manufactured by, licensed by, provided by, or distributed by the Sponsor for human use in this study.

Events meeting the AE definition

- Any abnormal laboratory test results (hematology, clinical chemistry, or urinalysis) or other safety assessments (eg, ECG, radiological scans, vital signs measurements), including those that worsen from baseline, considered clinically significant in the medical and scientific judgment of the investigator.
- Exacerbation of a chronic or intermittent pre-existing condition including either an increase in frequency and/or intensity of the condition.
- New conditions detected or diagnosed after study intervention administration even though it may have been present before the start of the study.
- Signs, symptoms, or the clinical sequelae of a suspected drug-drug interaction.
- Signs, symptoms, or the clinical sequelae of a suspected overdose of either study intervention or a concomitant medication.
- For all reports of overdose (whether accidental or intentional) with an associated AE, the AE term should reflect the clinical symptoms or abnormal test result. An overdose without any associated clinical symptoms or abnormal laboratory results is reported using the terminology "accidental or intentional overdose without adverse effect."
- Any new cancer or progression of existing cancer.

Events NOT meeting the AE definition

- Medical or surgical procedure (eg, endoscopy, appendectomy): the condition that leads to the procedure is the AE.
- Situations in which an untoward medical occurrence did not occur (social and/or convenience admission to a hospital).
- Anticipated day-to-day fluctuations of pre-existing disease(s) or condition(s) present or detected at the start of the study that do not worsen.
- Surgery planned prior to informed consent to treat a pre-existing condition that has not worsened.
- Refer to Section 8.4.7 for protocol-specific exceptions.

10.3.2 Definition of SAE

If an event is not an AE per definition above, then it cannot be an SAE even if serious conditions are met.

An SAE is defined as any untoward medical occurrence that, at any dose:

a. Results in death

b. Is life-threatening

- The term “life-threatening” in the definition of “serious” refers to an event in which the participant was at risk of death at the time of the event. It does not refer to an event, which hypothetically might have caused death, if it were more severe.

c. Requires inpatient hospitalization or prolongation of existing hospitalization

- Hospitalization is defined as an inpatient admission, regardless of length of stay, even if the hospitalization is a precautionary measure for continued observation. (Note: Hospitalization for an elective procedure to treat a pre-existing condition that has not worsened is not an SAE. A pre-existing condition is a clinical condition that is diagnosed prior to the use of an MSD product and is documented in the participant’s medical history.

d. Results in persistent or significant disability/incapacity

- The term disability means a substantial disruption of a person’s ability to conduct normal life functions.

- This definition is not intended to include experiences of relatively minor medical significance such as uncomplicated headache, nausea, vomiting, diarrhea, influenza, and accidental trauma (eg, sprained ankle) that may interfere with or prevent everyday life functions but do not constitute a substantial disruption.

e. Is a congenital anomaly/birth defect

- In offspring of participant taking the product regardless of time to diagnosis.

f. Other important medical events

- Medical or scientific judgment should be exercised in deciding whether SAE reporting is appropriate in other situations such as important medical events that may not be immediately life-threatening or result in death or hospitalization but may jeopardize the participant or may require medical or surgical intervention to prevent 1 of the other outcomes listed in the above definition. These events should usually be considered serious.

Examples of such events include invasive or malignant cancers, intensive treatment in an emergency room or at home for allergic bronchospasm, blood dyscrasias or convulsions that do not result in hospitalization, or development of drug dependency or drug abuse.

10.3.3 Additional Events Reported

Additional events that require reporting

In addition to the above criteria, AEs meeting either of the below criteria, although not serious per ICH definition, are reportable to the Sponsor.

- Is a cancer
- Is associated with an overdose

10.3.4 Recording AE and SAE

AE and SAE recording

- When an AE/SAE occurs, it is the responsibility of the investigator to review all documentation (eg, hospital progress notes, laboratory, and diagnostics reports) related to the event.
- The investigator will record all relevant AE/SAE information on the AE CRFs/worksheets at each examination.

- It is not acceptable for the investigator to send photocopies of the participant's medical records to the Sponsor in lieu of completion of the AE CRF page.
- There may be instances when copies of medical records for certain cases are requested by the Sponsor. In this case, all participant identifiers, with the exception of the participant number, will be blinded on the copies of the medical records before submission to the Sponsor.
- The investigator will attempt to establish a diagnosis of the event based on signs, symptoms, and/or other clinical information. In such cases, the diagnosis (not the individual signs/symptoms) will be documented as the AE/SAE.

Assessment of Intensity/Toxicity

- An event is defined as "serious" when it meets at least 1 of the predefined outcomes as described in the definition of an SAE, not when it is rated as severe.
- The investigator will make an assessment of intensity for each AE and SAE (and other reportable safety event) reported during the study and assign it to 1 of the following categories:
 - Mild: An event that is easily tolerated by the participant, causing minimal discomfort and not interfering with everyday activities (for pediatric studies, awareness of symptoms, but easily tolerated).
 - Moderate: An event that causes sufficient discomfort to interfere with normal everyday activities (for pediatric studies definitely acting like something is wrong).
 - Severe: An event that prevents normal everyday activities. An AE that is assessed as severe should not be confused with an SAE. Severe is a category utilized for rating the intensity of an event; and both AE and SAE can be assessed as severe (for pediatric studies, extremely distressed or unable to do usual activities).
- Injection-site redness/erythema or swelling from the day of vaccination through Day 5 (for adult participants) or Day 14 (for pediatric participants) postvaccination will be evaluated by maximum size.
- The investigator will make an assessment of toxicity for each AE and SAE (and other reportable event) reported during the study. Toxicity is only being assessed for adults 18 years of age and older. A toxicity grade will be assigned to injection-site AEs, specific systemic AEs, other systemic AEs, and vital sign (temperature) AEs as shown in the following tables. The toxicity grading scales used in this study are adapted from the "FDA Guidance for Industry: Toxicity Grading Scale for Healthy Adult and Adolescent Volunteers Enrolled in Preventive Vaccine Clinical Trials, September 2007."

Injection Site Reaction to Study Vaccine/Placebo^a	Grade 1	Grade 2	Grade 3	Grade 4
Injection-site AEs occurring Days 1 through 5 following receipt of study vaccine/placebo				
Pain/Tenderness	Does not interfere with activity	Repeated use of non-narcotic pain reliever >24 hours or interferes with activity	Any use of narcotic pain reliever or prevents daily activity	ER visit or hospitalization
Erythema/Redness	Size measured as B	Size measured as C or D	Size measured as E→	Necrosis or exfoliative dermatitis or results in ER visit or hospitalization
Induration/Swelling	Size measured as B	Size measured as C or D	Size measured as E→	Necrosis or ER visit or hospitalization
Other	Does not interfere with activity	Repeated use of non-narcotic pain reliever >24 hours or interferes with activity	Any use of narcotic pain reliever or prevents daily activity	ER visit or hospitalization
Any injection-site reaction that begins ≥ 6 days after receipt of study vaccine/placebo				
Pain/tenderness Erythema/Redness Induration/Swelling Other	Does not interfere with activity	Repeated use of non-narcotic pain reliever >24 hours or interferes with activity	Any use of narcotic pain reliever or prevents daily activity	ER visit or hospitalization

Abbreviations: AE=adverse event; ER=emergency room; eVRC=electronic vaccine report card; SAE=serious adverse event

^a Based upon information provided by the patient on the eVRC and verbally during VRC review. Erythema/Redness and Induration/Swelling are specific injection-site AEs with size designations of letters A through E→, based upon a graphic in the eVRC. Size A is not assigned a toxicity grade; however, injection-site AEs that measure size A should be reported as adverse experiences. If the participant has an ER visit or is hospitalized for any injection-site AE, that AE is to be assigned a toxicity grade of 4, regardless of the size measured.

Specific Systemic AE Toxicity Grading Scale

Systemic (General)	Mild (Grade 1)	Moderate (Grade 2)	Severe (Grade 3)	Potentially Life Threatening (Grade 4)
Headache	No interference with activity	Repeated use of non-narcotic pain reliever >24 hours or some interference with activity	Significant; any use of narcotic pain reliever or prevents daily activity	ER visit or hospitalization
Fatigue	No interference with activity	Some interference with activity	Significant; prevents daily activity	ER visit or hospitalization
Myalgia	No interference with activity	Some interference with activity	Significant; prevents daily activity	ER visit or hospitalization

Abbreviations: AE=adverse event; ER=emergency room

Other Systemic AE Toxicity Grading Scale

Systemic Illness ^a	Mild (Grade 1)	Moderate (Grade 2)	Severe (Grade 3)	Potentially Life Threatening (Grade 4) ^b
Illness or clinical AE (as defined according to applicable regulations)	No interference with activity	Some interference with activity not requiring medical intervention	Prevents daily activity and required medical intervention	ER visit or hospitalization

Abbreviations: AE=adverse event; ER=emergency room; eVRC=electronic vaccine report card; SAE=serious adverse event

^a Based upon information provided by the patient on the eVRC and verbally during the eVRC review during the primary safety follow-up period. For SAEs reported beyond the primary safety follow-up period, grading will be based upon the initial report and/or follow-up of the event.

^b AEs resulting in death will be assessed as Grade 4

Vital Sign (Temperature) Toxicity Grading Scale

Vital Signs ^a	Mild (Grade 1)	Moderate (Grade 2)	Severe (Grade 3)	Potentially Life Threatening (Grade 4)
Fever (°C) ^b (°F) ^b	38.0 to 38.4 100.4 to 101.1	38.5 to 38.9 101.2 to 102.0	39.0 to 40.0 102.1 to 104.0	>40.0 >104.0

^a Participant should be at rest for all vital sign requirements

^b Oral temperature; no recent hot or cold beverages or smoking

Assessment of causality

- Did the Sponsor’s product cause the AE?
- The determination of the likelihood that the Sponsor’s product caused the AE will be provided by an investigator who is a qualified physician. The investigator’s signed/dated initials on the source document or worksheet that supports the causality noted on the AE form, ensures that a medically qualified assessment of causality was done. This initialled document must be retained for the required regulatory time frame. The criteria below are intended as reference guidelines to assist the investigator in assessing the likelihood of a relationship between the test product and the AE based upon the available information.
- **The following components are to be used to assess the relationship between the Sponsor’s product and the AE;** the greater the correlation with the components and their respective elements (in number and/or intensity), the more likely the Sponsor’s product caused the AE:
 - **Exposure:** Is there evidence that the participant was actually exposed to the Sponsor’s product such as: reliable history, acceptable compliance assessment (diary, etc.), seroconversion or identification of vaccine virus in bodily specimen?

- **Time Course:** Did the AE follow in a reasonable temporal sequence from administration of the Sponsor's product? Is the time of onset of the AE compatible with a vaccine-induced effect?
- **Likely Cause:** Is the AE not reasonably explained by another etiology such as underlying disease, other drug(s)/vaccine(s), or other host or environmental factors?
- **Rechallenge:** Was the participant re-exposed to the Sponsor's product in the study?
- If yes, did the AE recur or worsen?
- If yes, this is a positive rechallenge.
- If no, this is a negative rechallenge.

(Note: This criterion is not applicable if: (1) the initial AE resulted in death or permanent disability, or (2) the study is a single-dose vaccine study); or (3) Sponsor's product(s) is/are used only 1 time.)

NOTE: IF A RECHALLENGE IS PLANNED FOR AN AE THAT WAS SERIOUS AND MAY HAVE BEEN CAUSED BY THE SPONSOR'S PRODUCT, OR IF RE-EXPOSURE TO THE SPONSOR'S PRODUCT POSES ADDITIONAL POTENTIAL SIGNIFICANT RISK TO THE PARTICIPANT THEN THE RECHALLENGE MUST BE APPROVED IN ADVANCE BY THE SPONSOR CLINICAL DIRECTOR, AND IF REQUIRED, THE IRB/IEC.

- **Consistency with study intervention profile:** Is the clinical/pathological presentation of the AE consistent with previous knowledge regarding the Sponsor's product or drug class pharmacology or toxicology?
- The assessment of relationship will be reported on the CRFs /worksheets by an investigator who is a qualified physician according to his/her best clinical judgment, including consideration of the above elements.
- Use the following scale of criteria as guidance (not all criteria must be present to be indicative of a Sponsor's product relationship).
- Yes, there is a reasonable possibility of Sponsor's product relationship:
 - There is evidence of exposure to the Sponsor's product. The temporal sequence of the AE onset relative to the administration of the Sponsor's product is reasonable. The AE is more likely explained by the Sponsor's product than by another cause.
- No, there is not a reasonable possibility of Sponsor's product relationship:
 - Participant did not receive the Sponsor's product OR temporal sequence of the AE onset relative to administration of the Sponsor's product is not reasonable OR the AE

is more likely explained by another cause than the Sponsor's product. (Also entered for a participant with overdose without an associated AE.)

- For each AE/SAE, the investigator must document in the medical notes that he/she has reviewed the AE/SAE and has provided an assessment of causality.
- There may be situations in which an SAE has occurred and the investigator has minimal information to include in the initial report to the Sponsor. However, it is very important that the investigator always make an assessment of causality for every event before the initial transmission of the SAE data to the Sponsor.
- The investigator may change his/her opinion of causality in light of follow-up information and send an SAE follow-up report with the updated causality assessment.
- The causality assessment is 1 of the criteria used when determining regulatory reporting requirements.

Follow-up of AE and SAE

- The investigator is obligated to perform or arrange for the conduct of supplemental measurements and/or evaluations as medically indicated or as requested by Sponsor to elucidate the nature and/or causality of the AE or SAE as fully as possible. This may include additional laboratory tests or investigations, histopathological examinations, or consultation with other health care professionals.
- New or updated information will be recorded in the CRF.
- The investigator will submit any updated SAE data to the Sponsor within 24 hours of receipt of the information.

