8.3.4 Safety Assessments and Use of the eVRC

All participants will be observed for 30 minutes after each vaccination for any immediate reactions. If any immediate AEs are observed during this period, the time at which the event occurred within this time frame, as well as the event itself, any concomitant medications that were administered, and resolution of the event, must be recorded on the appropriate eCRF.

Adult participants will use the eVRC (Section 8.1.9) to document the following information:

- Oral body temperatures measured Day 1 (day of vaccination) through Day 5 postvaccination;
- Solicited injection-site AEs (redness/erythema, swelling, and tenderness/pain) Day 1 through Day 5 postvaccination;
- Solicited systemic AEs (muscle pain/myalgia, joint pain/arthralgia, headache, and tiredness/fatigue) Day 1 through Day 14 postvaccination;

- Any other injection-site or systemic AEs Day 1 through Day 14 postvaccination; and
- Concomitant medications and nonstudy vaccinations Day 1 to Day 14 postvaccination.

Pediatric participants or the participant's legally acceptable representative will use the eVRC (Section 8.1.9) to document the following information:

Pediatric participants 3 to <18 years of age

- Body temperatures measured Day 1 (day of vaccination) through Day 7 postvaccination; Day 8 through Day 14 postvaccination if fever is suspected
- Solicited injection-site AEs (redness/erythema, swelling, tenderness/pain, and hard lump) Day 1 through Day 14 postvaccination
- Solicited systemic AEs (muscle pain/myalgia, joint pain/arthralgia, headache, tiredness/fatigue, and hives or welts) Day 1 through Day 14 postvaccination
- Any other injection-site or systemic AEs Day 1 through Day 14 postvaccination
- Use of any analgesic or antipyretic on the day of vaccination.
- Concomitant medications and nonstudy vaccinations Day 1 to Day 14 postvaccination.

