9.1 Statistical Analysis Plan Summary

Key elements of the statistical analysis plan are summarized below; the comprehensive plan is provided in Sections 9.2 through 9.12.

Study Design Overview	A Phase 3, Randomized, Double-Blind, Active Comparator-Controlled, Multicenter Clinical Trial to Evaluate the Safety, Tolerability, and Immunogenicity of V114 in Recipients of Allogeneic Hematopoietic Stem Cell Transplant (PNEU-STEM)
Treatment Assignment	
Approximately 250 adult participants and approximately 50 pediatric participants (3 years of age and older) will be randomized, with approximately 150 participants in each intervention group.
 
Participants will be randomly assigned in a 1:1 ratio to V114 or Prevnar 13™, respectively. Randomization will be stratified into 12 groups based on (1) use of systemic steroids within 14 days before randomization (Day 1) (yes or no) and (2) age category (3 to <18 years, 18 to 49 years and ≥50 years) (3) haploidentical donor status (yes or no) as described in Section 6.3.2.

Analysis Populations	
Immunogenicity: Per-Protocol (PP)
 
Safety: All Participants as Treated (APaT)

Primary Endpoint(s)	
Immunogenicity:
 
 • Serotype-specific IgG GMCs at 30 days following the 3rd dose of V114 or Prevnar 13™ (Day 90) 
Safety: Following any of the 3 doses of V114 and any of the 3 doses of Prevnar 13™ for adults (≥18 years of age):
 
 • Proportion of participants with solicited injection-site AEs (redness/erythema, swelling, tenderness/pain) from Day 1 through Day 5 postvaccination • Proportion of participants with solicited systemic AEs (muscle pain/myalgia, joint pain/arthralgia, headache, and tiredness/fatigue) from Day 1 through Day 14 postvaccination • Proportion of participants with vaccine-related SAEs from Day 1 postvaccination to Month 12 following allo-HSCT 
Following any of the 3 doses of V114 and any of the 3 doses of Prevnar 13™ for pediatrics (3 to <18 years of age):
 
 • Proportion of participants with solicited injection-site AEs (redness/erythema, swelling, tenderness/pain, and hard lump) from Day 1 through Day 14 postvaccination

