9.6.2 Statistical Methods for Safety Analyses

Safety and tolerability will be assessed by clinical review of all relevant parameters separately for adults and pediatric participants including AEs and postvaccination temperature measurements.

The analysis strategy of safety parameters is summarized in Table 6. The proportion of participants with solicited injection-site AEs (redness/erythema, swelling, tenderness/pain from Day 1 to Day 5 postvaccination for adult participants, and redness/erythema, swelling, tenderness/pain, and hard lump from Day 1 to Day 14 postvaccination for pediatric participants) and solicited systemic AEs (muscle pain/myalgia, joint pain/arthritis, headache, and tiredness/fatigue from Day 1 to Day 14 postvaccination for adult participants, and muscle pain/myalgia, joint pain/arthritis, headache, tiredness/fatigue, and hives and

welts for pediatric participants) will be provided along with the corresponding within-group 95% CIs (based on the exact binomial method proposed by Clopper and Pearson [Clopper, C. J. and Pearson, E. S. 1934]). In addition, the broad AE categories consisting of the proportion of participants with any AE, a vaccine-related AE, a SAE, an AE which is both vaccine-related and serious, discontinuation due to an AE, and the proportion of participants who died will be summarized in the same manner separately for adult and pediatric participants. The proportion of participants with maximum temperature measurements meeting the Brighton Collaboration cut points (from Day 1 through Day 5 postvaccination for adult participants, and Day 1 through Day 7 for pediatric participants) will also will be provided along with the corresponding within-group 95% CIs. Point estimates by vaccination group will be provided for all other safety parameters (specific AE terms and system organ class terms).

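### Arthralgia, a solicited adult systemic AE, has no row in the specific toxicity table and falls to a scale that leaves two combinations ungraded; the severity data collected on solicited AEs enter no planned analysis

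*Combined protocol and SAP*

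**What the plan says.** Section 8.3.4 has adults record on the eVRC: "Solicited systemic AEs (muscle pain/myalgia, joint pain/arthralgia, headache, and tiredness/fatigue) Day 1 through Day 14 postvaccination". Section 9.1 makes the same four terms a primary safety endpoint: "Proportion of participants with solicited systemic AEs (muscle pain/myalgia, joint pain/arthralgia, headache, and tiredness/fatigue) from Day 1 through Day 14 postvaccination".

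Section 10.3.4 sets up three severity measures. Every AE gets an intensity rating (mild, moderate or severe). Redness and swelling are evaluated by maximum size. On the third measure the section says: "The investigator will make an assessment of toxicity for each AE and SAE (and other reportable event) reported during the study". It limits that measure by age: "Toxicity is only being assessed for adults 18 years of age and older". Four scales are offered: injection-site, specific systemic, other systemic and temperature.

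The table headed "Specific Systemic AE Toxicity Grading Scale" has rows for headache, fatigue and myalgia. There is no row for arthralgia, and the text does not say which scale arthralgia uses. On the Other Systemic scale, Grade 2 is "Some interference with activity not requiring medical intervention" and Grade 3 is "Prevents daily activity and required medical intervention".

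On analysis, Sections 9.4.2 and 9.6.2 and Table 6 list proportions of participants with each solicited AE, the broad AE categories (any, vaccine-related, serious, both vaccine-related and serious, discontinuation, death), and maximum temperature by Brighton cut points. For the remainder, Section 9.6.2 states: "Point estimates by vaccination group will be provided for all other safety parameters (specific AE terms and system organ class terms".

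**The concern.** Two solicited symptoms reported on the same card are graded by different rules. Myalgia that stops daily activity is Grade 3. Arthralgia that does the same, with no medical intervention, meets no grade's definition, although a grade is required for every adult AE. Sites would have to improvise, and may do so differently. The same gap touches every other adult systemic AE graded on that scale.

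The second matter is independent of the first. The first primary objective concerns safety and tolerability, yet the solicited-AE results will say only how many participants had each reaction at least once. Two groups with the same proportion reporting a reaction but different severity would look alike in the planned tables, even though the data to tell them apart are collected. The Swedish appendix (Section 10.7.1.1) rests part of its benefit/risk argument on earlier studies finding no difference in either the frequency or the severity of AEs. As written, this plan would update mainly the frequency part.

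**Working it through.** The plan states no figure on this point, so there is none to reproduce. The check is a cross-reading of the tables plus one multiplication.

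**Step 1: solicited terms against grading rows.** Section 8.3.4 solicits four adult systemic terms: myalgia, arthralgia, headache and fatigue. The specific systemic table has three rows: headache, fatigue and myalgia. The unmatched term is arthralgia. It is neither an injection-site nor a temperature event, so the only scale left is Other Systemic. This is an inference by elimination.

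**Step 2: is the fallback scale exhaustive?** Cross interference with activity (none, some, prevents) with medical intervention (no, yes), giving 3 × 2 = 6 combinations. ER visits, hospitalization and death are left out because they are Grade 4.

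| Interference | Intervention | Other Systemic scale | Myalgia row |
|---|---|---|---|
| None | No | 1 | 1 |
| None | Yes | 1 | 1 |
| Some | No | 2 | 2 |
| Some | Yes | no grade | 2 |
| Prevents | No | no grade | 3 |
| Prevents | Yes | 3 | 3 |

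Other Systemic leaves 2 of 6 combinations ungraded; the myalgia row leaves 0 of 6.

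**Step 3: is the gap intended?** Section 10.3.4 says explicitly when a finding gets no grade: the smallest lesion size, A, is reported but not graded. Nothing similar is said about these two combinations. The headache and injection-site pain rows join their criteria with an or, which avoids the problem.

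**Step 4: does another measure cover arthralgia?** Yes. The intensity scale in Section 10.3.4 applies to every AE in both cohorts and rests on interference with activity, with no intervention condition. Arthralgia that prevents normal activity is severe on that scale, just as myalgia is.

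**Step 5: where do the severity data go?** Sections 3, 9.1, 9.4.2, 9.6.2 (with Table 6) and 9.10 contain no analysis that uses intensity, maximum size or toxicity grade. The nearest items are the Brighton temperature cut points and the SAE, death and discontinuation categories.

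**Step 6: scale.** Inputs are 125 V114 adults (Section 9.9.2) and earlier adult V114 joint-pain rates of 7% and 17% (Section 10.7.1.1).

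- 125 × 0.07 = 8.75, about 9
- 125 × 0.17 = 21.25, about 21

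These count all joint pain, most of which may be gradable. The documents give no split by interference and intervention, so the number in the two ungraded combinations cannot be calculated.

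**The case against.** The strongest reply is that the two halves limit each other: if no toxicity grade enters an endpoint, a gap in that grade cannot bias any planned estimate. That stands. A reader might infer that a primary endpoint is distorted, but the planned proportions count occurrence, which the gap does not touch.

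A reader might also infer that severe arthralgia goes unrated. It does not, because the intensity scale rates it without a gap. Only the adult toxicity grade is affected.

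Nor is it right that the safety analysis ignores severity altogether. Vaccine-related SAEs are part of the same primary objective; hospitalization is both Grade 4 and an SAE criterion; discontinuations, deaths and temperature cut points are analysed with confidence intervals. What is missing is any use of intensity, size or grade for solicited AEs.

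The second ungraded combination should be read narrowly. Grade 2 excludes events requiring medical intervention, and joint pain self-treated with an analgesic need not have required any, so it can still be Grade 2.

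It can also be said that the safety objectives are within-group, with no hypothesis tests and no between-group safety contrast. That is correct, and severity summaries would be descriptive too. It does not explain leaving out collected data that bear on tolerability.

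Finally, Section 9 allows changes before unblinding through a supplemental SAP. However, the text defers to it only exploratory methods, the cLDA details and the subgroup details. It commits to no severity table.

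**Conclusion.** The point holds as two limited defects. First, the adult toxicity scales omit one of four solicited systemic AEs, and the scale it falls to leaves 2 of 6 combinations ungraded, against 0 of 6 under the myalgia criteria. This harms the consistency of a required data field and of any later severity table, but no planned proportion. Second, apart from temperature cut points and the SAE, death and discontinuation categories, no planned safety analysis uses the severity data collected, so solicited-AE tolerability is described as yes/no only.

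The first part assumes that arthralgia belongs on the Other Systemic scale, which is the only reading the text leaves open. The figure of about 9 to 21 V114 adults with any joint pain assumes that rates from non-HSCT adults given a single dose carry over to a three-dose regimen in transplant recipients. Section 10.7.1.1 notes more frequent reactions with repeated dosing, so the true number could be higher. It would be wrong to read 9 to 21 as the number who cannot be graded; that number is unknown.

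**What to change.** 1. Add an arthralgia row to the specific systemic toxicity table in Section 10.3.4, using the existing myalgia criteria.
2. Have the sponsor reconcile the Grade 2 and Grade 3 criteria of the Other Systemic scale so that every event can be assigned a grade. There are several ways to do this, and the choice is the sponsor's.
3. Add to Table 6, for each solicited AE, the distribution of maximum intensity in both cohorts; for redness and swelling, the maximum size; and for adults, the proportion with Grade 3 or higher with its exact (Clopper-Pearson) within-group 95% CI, the method Section 9.6.2 already uses.

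The cost is one appendix edit and a few extra table rows. Intensity, size and grade are already collected, so no new assessment is needed. Settling this before unblinding avoids post hoc decisions about events that fit no grade.
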